#### **4.2. Missing/Incomplete Start and Stop Dates**

For the purpose of inclusion in tables, incomplete start and stop dates and times for AEs and prior/concomitant medications will be imputed as follows:

Missing start dates (where UK, UNK and UNKN indicate unknown or missing day and month respectively) will be handled as follows:

- UK-MMM-YYYY:
  - If the month and year are different from the month and year of the first dose of study drug, assume 01-MMM-YYYY.
  - If the month and year are the same as the first dose of study drug month and
    - the end date (after any imputation) is on or after the first dose of study drug, then the start date is assumed to be the date of the first dose of study drug.
    - the end date (after any imputation) is prior to the first dose of study drug, then assume the end date for the start date.
- DD-UNK-YYYY/UK-UNK-YYYY:
  - If the year is different from the year of first dose of study drug, assume 01-JAN-YYYY of the collected year.
  - If the year is the same as the first dose of study drug year and
    - the end date (after any imputation) is on or after the first dose of study drug, then the start date is assumed to be the date of the first dose of study drug.
    - the end date (after any imputation) is prior to the first dose of study drug, then the start date is assumed to be the end date for the start date.

If the start date is not recorded on eCRF then no date imputation will be performed.

Missing start times will be imputed as follows: If the missing time of an actual or imputed start date is the same as a study drug dosing date, the dosing time will be used as the imputed time. Otherwise, the earliest possible time of the actual or imputed start date (i.e. 00:01) will be used as the imputed time.

Missing stop dates (where UK and UNK indicate unknown or missing day and month respectively) will be handled as follows:

- UK-MMM-YYYY: Stop date is assumed to be the last day of the month;
- DD-UNK-YYYY/UK-UNK-YYYY: Stop date is assumed to be 31-DEC-YYYY.

If a subject dies during the study, the stop date will be imputed as the date of death if the imputed stop date is after date of death.

Missing stop times will be imputed as the latest possible time of the actual or imputed stop date (i.e. 23:59).

#### **4.3. Sample Size**

Approximately 24 subjects are planned in 2 cohorts. Each cohort will include 12 subjects (9 on LTI-03 and 3 on placebo). Selection of sample size is based on prior experience to ensure that the safety and tolerability of LTI-03 will be adequately assessed while minimizing unnecessary subject exposure. With 18 subjects receiving LTI-03 there is a 60% chance of detecting an adverse event (AE) with a true incidence rate of 5% and an 85% chance of detecting a more common AE with a true incidence rate of 10%.

#### **4.4. Randomization and Blinding**

Subjects will be randomized to receive LTI-03: placebo in sequential cohorts, as per the study design. Randomization codes and unique subject identification numbers will be generated by the Interactive Voice Response System (IVRS). All study staff will remain blinded to study drug assignment throughout the trial.

An unblinded team of Biostatistics personnel will be set up to handle unblinded data until the study is unblinded after data lock.

#### **4.5. Analysis Sets**

The following analyses sets will be used for the various analyses outlined in this SAP.

##### **4.5.1. Enrolled Set**

The Enrolled Set will consist of all subjects who signed the informed consent form (ICF), to include screen failures.

A screen failure is defined as a subject who consents to participate in the study but is not subsequently randomized.

##### **4.5.2. Randomized Set**

The Randomized Set will consist of all subjects who were enrolled and randomized to study drug.

#### **4.5.3. Safety Set**

The Safety Set will consist of all subjects randomized to study drug and received at least one dose of study drug. The Safety Set will be used for all safety analyses and subjects will be analyzed according to the study drug actually received.

#### **4.5.4. Pharmacokinetics (PK) Set**

The PK Set will consist of all subjects who receive at least one dose of LTI-03 and have at least one evaluable PK concentration.

#### **4.5.5. Pharmacodynamics (PD) Set**

The PD Set will consist of all subjects who received at least one dose of LTI-03 and have at least one measured value at a scheduled PD time point after the start of dosing for at least one PD analyte.

### **5. Subject Disposition and Protocol Deviations**

#### **5.1. Subject Disposition**

Subjects will be summarized by the number and percent of subjects dosed, completed the study, discontinued from the study (with discontinuation reasons), completed treatment, and discontinued from treatment (with treatment discontinuation reasons). The number of subjects randomized (i.e., subjects with a randomization date/time/number recorded on the eCRF) will also be summarized. Subject disposition summary will be presented by treatment (active treatments, active treatment total, and pooled placebo) and overall.

All subject disposition data recorded on the eCRF, including for subjects not randomized will be listed by subject using the Enrolled Set.

#### **5.2. Protocol Deviations**

All protocol deviations will be recorded and documented according to the Study Deviation Rules document in PPD's Clinical Trial Management System (CTMS) system. Once the deviations have been finalized, a MS Excel file with all deviations will be converted into a SAS dataset and used as the source for the SDTM DV domain to generate a listing. Protocol deviations will be tabulated by severity (i.e., Major/Minor). The summary table will include the number of subjects reporting protocol deviations and as a percent of the number of subjects dosed by treatment (active treatments, active treatment total, and pooled placebo) and overall. If a subject reports protocol deviations at more than one level of severity, both categories will be summarized during analysis.

The following definitions will be used:

- Major protocol deviations are defined as those deviations with substantial effect on patient safety or data integrity.
- Minor protocol deviations are defined as those deviations with non-substantial effect on patient safety or data integrity.
- Significant protocol deviations are defined as those deviations which affect the analysis population.

- Non-significant protocol deviations are defined as those deviations which do not affect the analysis population.

The summary and listing of the protocol deviations will be provided for the Safety Set.

## **6. Demographics and Baseline Characteristics**

### **6.1. Demographics and Baseline Characteristics**

The number and percentage of subjects by sex (Male, Female), reproductive status (Of Child-bearing Potential, Surgically Sterile, Post-menopausal), race (White, Black or African American, Asian, American Indian or Alaska Native, Native Hawaiian or Other Pacific Islander, Not Reported, Unknown and Other) and ethnicity (Hispanic or Latino, Not Hispanic or Latino, Not Reported and Unknown) will be summarized.

The baseline characteristics consist of age (years), baseline height (cm), baseline weight (kg), baseline body mass index (BMI) ( $\text{kg}/\text{m}^2$ ), number of cigarettes (or the equivalent) per day (pack-years (applicable only to subjects with past and/or current tobacco use)), and Diffusion Capacity of the Lungs for Carbon Monoxide (DLCO) (measured value only, in units of  $\text{mmol}/\text{min}/\text{kPa}$ ), baseline spirometry (FVC), baseline LCQ total score and baseline cough VAS score. Demographics and baseline characteristics will be summarized descriptively.

Body mass index is calculated as (body weight in kilograms) / (height in meters). A subject's age in years is calculated using the date of the informed consent and date of birth.

Cigarette consumption will be calculated in pack-years using: (the number of cigarettes smoked per day/20) \* number of years smoked.

The summary of subject demographics and baseline characteristics will be presented by treatment (active treatments, active treatment total, and pooled placebo) and overall. Subject demographics and baseline characteristics will be listed. The summary and listing of demographics and baseline characteristics will be provided for the Safety Set.

### **6.2. Medical History**

#### **6.2.1. General Medical History**

Medical history will be coded using the Medical Dictionary for Regulatory Activities (MedDRA) version 26.0 or higher by system organ class (SOC) and preferred term (PT).

Subject medical history data including specific details as collected in the eCRF will be presented in a listing for the Safety Set.

#### **6.2.2. Disease-Specific History**

Details of IPF diagnosis (diagnostic method and date of test) will be listed for the Safety Set.

### **6.3. Inclusion and Exclusion Criteria**

The details of the inclusion and exclusion criteria can be found in Sections 4.1.1 and 4.1.2 of the study protocol. The status of eligibility criteria met, inclusion criteria not met, or exclusion criteria met details will be listed for the Enrolled Set.

## 7. Treatments and Medications

### 7.1. Prior and Concomitant Medications

All medications (including over-the-counter medicines, herbal treatments, supplements, and vitamins) administered within 30 days of the Screening Visit through Study Day 21 will be recorded on the Case Report Form (CRF), using generic names when possible.

Prior and concomitant medication will be coded according to the latest World Health Organization Drug Dictionary (WHODD) version March, 2023 or later. Missing/partial start and stop dates will be imputed as specified in [Section 4.2](#).

The listing of prior and concomitant medications will be provided for the Safety Set. All prior and concomitant medications will be presented in the same listing.

#### 7.1.1. Prior Medications

A prior medication is defined as a medication that ends prior to the first study drug administration.

#### 7.1.2. Concomitant Medications

A concomitant medication is defined as a medication that ends at the time of or after the first study drug administration.

### 7.2. Concomitant Procedures

All concomitant procedures recorded during the study will be listed. The listing will be provided for the Safety Set.

### 7.3. Extent of Exposure and Treatment Compliance Rate

Exposure to study drug is defined as administration of any amount of study drug. Duration of exposure is defined as the total number of days a subject is exposed to study drug and will be presented as the total number of days from the first dose date and time (Day 1) to the last dose date and time (date of last dose minus the date of first dose + 1) as recorded in the eCRF.

Drug compliance over the total dosing period will be assessed as the rate of compliance. The rate of compliance (%) will be calculated as follows and recorded on the eCRF: [(number of capsules used/number of capsules expected to be used)]\*100.

The extent of exposure and rate of compliance will be summarized by treatment (active treatment arms, total of active arms, pooled placebo) and overall. A listing of exposure and compliance rate data will be presented.

The summary table and listing of exposure and compliance rate will be provided for the Safety Set.

## 8. Safety Analysis

Safety will be evaluated through continuous monitoring of AEs, physical examinations, vital signs, clinical laboratory measurements, spirometry, and ECGs.

Safety summaries and listings will be presented for the Safety Set.

## 8.1 Adverse Events

According to the International Council for Harmonization (ICH) guideline for GCP, an AE is any untoward medical occurrence in a subject or clinical investigation subject administered a pharmaceutical product, and which does not necessarily have to have a causal relationship with the treatment. An AE can therefore be any of the following:

- Any unfavorable and unintended sign (including an abnormal laboratory finding), symptom, or disease temporally associated with the use of a medicinal product, whether or not considered related to the medicinal product.
- Any new disease or exacerbation of an existing disease (a worsening in the character, frequency, or severity of a known condition).
- Recurrence of an intermittent medical condition (e.g., headache) not present at baseline.
- Any deterioration in a laboratory value or other clinical test (e.g., ECG) that is associated with symptoms or leads to a change in study treatment or concomitant treatment or discontinuation from study drug.
- Adverse events that are related to a protocol-mandated intervention, including those that occur prior to assignment of study treatment (e.g., Screening invasive procedures such as biopsies).

Adverse events will be coded using the current version of Medical Dictionary for Regulatory Activities (MedDRA® Version 26.0 or higher). Missing/partial AE dates and times will be imputed as specified in [Section 4.2](#). In general, summaries will be provided for the Safety Set and presented by SOC, PT and treatment (active treatments, active treatment total, and pooled placebo) and overall. Participants will be counted only once within each SOC or PT.

All AEs will be presented in a listing.

### 8.1.1. Incidence of Treatment-Emergent Adverse Events

AEs which begin or increase in severity or frequency at or after the administration of first dose of study drug are to be considered as TEAEs.

An overall summary of TEAEs will include the number and percentage of participants with at least one TEAE, any TEAE with CTCAE severity Grade 3 or higher, any related TEAE, any serious TEAE, any fatal TEAE, and any TEAEs leading to discontinuation of study drug.

The number and percentage of participants with TEAEs and the total number of TEAEs will be summarized by SOC and PT for each treatment (active treatments, active treatment total, and pooled placebo) and overall.

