1.1.1.3 Clinical Background

LTI-03 was initially assessed in a Phase 1a study, LTI-03-1001: A Randomized, Double-Blind, Placebo-Controlled, Phase 1a, First-in-Man, Single Ascending Dose (SAD) and Multiple Ascending Dose (MAD) Safety, Tolerability and PK Study of a Cav-1-Scaffolding-Protein-Derived Peptide (LTI-03) in Healthy Adult Subjects. Twenty-four subjects were administered LTI-03 in 4 SAD cohorts at single doses of 10 mg, 40 mg, and 80 mg. At the 80 mg dose, subjects in 1 cohort were administered 4 20 mg capsules by inhalation and in a second cohort subjects at this 80 mg dose were administered 8 10 mg capsules by inhalation. Eight subjects in the combined SAD cohorts were administered placebo. In the SAD cohorts, 21 of the 24 subjects (88%) who were administered LTI-03 experienced treatment -emergent adverse events (TEAE), the most frequent of which were mild dry coughs that were considered to be related to LTI-03.

Twenty-nine subjects were administered LTI-03 by inhalation daily for up to 14 days in 5 MAD cohorts at doses of 2.5 mg once daily (QD), 5 mg QD, 5 mg twice daily (BID), 20 mg QD and 40 mg QD. The 2 higher dose MAD cohorts, 20 mg QD and 40 mg QD, were completed before the lower dose cohorts. The 3 lower doses were well tolerated. The most common TEAE in these 3 cohorts was a mild dry cough. During dosing in the 40 mg QD MAD cohort 1 subject developed severe TEAEs and two other subjects developed moderate TEAEs secondary to pulmonary airflow limitations (decreased forced expiratory volume 1 [FEV₁] and FEV₁/FVC ratios) that appeared to

be due to reversible airway obstruction. These events were considered to be dose limiting and related to LTI-03. There was no evidence that the TEAEs in the 3 subjects described previously were secondary to an allergic response. In the 20 mg QD MAD cohorts there were mild decreases in FEV₁ in two subjects that were not associated with TEAEs. These were not considered to be dose limiting. There were no serious adverse events (SAEs). All TEAEs were resolved 7 days after the treatment period. Further details can be found in the IB.

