8.4 Collection and Reporting of Adverse Events

8.4.1 Initial Reporting of Adverse Events

Any event occurring prior to administration of the first dose of study drug will be recorded in the Medical History on eCRF unless the AE is serious and related to a protocol-mandated intervention as per Section 8.2.1. A pre-existing medical condition should be recorded as an AE only if the frequency, severity, or character of the condition worsens during the study.

All AEs from time of first dose through the EOS will be collected, regardless of relationship to study drug.

A clinically relevant deterioration in laboratory assessments or other clinical findings, as assessed by the Investigator, is considered an AE, and must be recorded on the AE CRF if it meets the reporting time frames above. In addition, an abnormal test finding will be classified as an AE if one or more of the following criteria are met:

- The test finding is accompanied by clinically significant symptoms.

- The test finding necessitates additional diagnostic evaluation(s) or medical / surgical intervention, including additional concomitant drug treatment or other therapy. Note: simply repeating a test finding, in the absence of any of the other listed criteria, does not constitute an AE.
- The test finding leads to a change in study drug dosing or discontinuation of subject participation in the clinical research study.
- The test finding is considered an AE by the Investigator.

Wherever possible, a specific disease or syndrome rather than individual associated signs and symptoms should be identified. However, if an observed or reported sign or symptom is not associated with a specific disease or syndrome, the individual sign or symptom should be recorded as a separate AE. Laboratory data are to be collected as stipulated in this protocol. Clinical syndromes associated with laboratory abnormalities are to be recorded as appropriate (e.g., diabetes mellitus rather than hyperglycemia).

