8.8 Stopping Rules

Safety data will be reviewed on an ongoing basis by the Sponsor's Medical Officer and the CRO Medical Monitor (Section 3) who will monitor subject safety during study conduct and can make decisions regarding individual subject drug, group/cohort treatment, and/or subsequent dosing regimens. The grading of events can be used to help determine these decisions, taking into consideration the subject's baseline parameters and the possibility for differences based on demographics.

Potential safety signals that will trigger a meeting of the Sponsor and CRO medical personnel, and subsequent written recommendation about study conduct include the following:

- Any SAE considered to be related to study drug
- Any related clinical NCI CTCAE \geq grade 3 (severe) AE
- Any unrelated similar SAE or clinical NCI CTCAE \geq grade 3 (severe) AE in ≥ 2 subjects. For example, wheezing and chest tightness would be considered similar because they may both be related to airway obstruction.

As noted in Section 6.14.1 study drug will be discontinued in subjects with a decrease from Baseline in FEV1 of $\geq 15\%$ associated with a decrease from Baseline in the FEV1/FVC ratio.

Related AEs or suspected adverse drug reactions means that a causal relationship between a medicinal product and an AE is at least a reasonable possibility, i.e., there is evidence to suggest a causal relationship.

When a potential safety signal as defined above occurs, enrollment will be halted pending review by the Sponsor Medical Officer and CRO Medical Monitor and study treatment will be stopped in the individual experiencing the safety signal AE. All potential safety signals will be reviewed within 7 days by the Sponsor Medical Officer and CRO Medical Monitor that could recommend:

- Re-start subject enrollment. A protocol amendment summarizing available data and justification will be required to continue enrollment at the dose level associated with a stopping rule or any higher dose.

- Add a new lower dose cohort
- Add more subjects to a cohort without dose limiting toxicities
- Continued pausing of enrollment
- Permanently discontinuing enrollment into the study

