9.2 Study Hypotheses

The primary endpoint of the study is safety. No formal statistical hypotheses will be tested.

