## **3.2. Study Endpoints**

### **3.2.1. Primary Endpoint**

- Incidence of Treatment Emergent Adverse Events (TEAE).

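### The planned TEAE tables have no grouped row for airflow limitation, so the number of subjects per dose with the known dose-limiting harm is not guaranteed to appear in any of them

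*SAP*

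**What the plan says.** **Endpoint and tables.** TEAE incidence is the primary endpoint (SAP 3.2.1), and the analysis is descriptive: "No formal statistical hypotheses will be tested" (Protocol 9.2). SAP 8.1.1 plans an overall summary with rows for any TEAE, Grade 3 or higher, related, serious, fatal, and leading to discontinuation. Below that, "The number and percentage of participants with TEAEs and the total number of TEAEs will be summarized by SOC and PT". SAP 8.1.2 and 8.1.3 repeat the SOC and PT layout for related TEAEs and for maximum severity. SAP 8.1 counts a subject once per SOC and once per PT. No grouped term, event of special interest or MedDRA query is defined.

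**The known harm.** Protocol 1.1.1.3 reports that in the 40 mg once-daily cohort one subject had severe TEAEs and two others "developed moderate TEAEs secondary to pulmonary airflow limitations". These events were judged dose limiting and drug related.

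**How cases are recorded.** Protocol 8.4.1 asks for a diagnosis where possible. Where none can be assigned, "the individual sign or symptom should be recorded as a separate AE".

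**Where the protocol groups terms.** Protocol 8.8 notes that "wheezing and chest tightness would be considered similar because they may both be related to airway obstruction". This example belongs to one trigger only, the one for unrelated similar SAEs or Grade 3 or higher AEs in two or more subjects.

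**The concern.** A central safety question for this trial is whether its doses produce in IPF patients the airflow limitation seen at higher doses in healthy volunteers. A reader of the report will want to know how many of the 9 subjects on each dose had such an event, and how many on placebo.

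The planned tables need not answer that. One subject may be coded to wheezing, a second to chest tightness and a third to a fall in FEV1. All three entries can be valid under Protocol 8.4.1, and each gets its own row. Adding the rows does not recover the number of subjects, because a subject with two terms is counted in both. PT rows of 2/9 and 1/9 may stand for two people or three. The by-subject AE listing allows the count to be rebuilt, but without a list set in advance the terms would be chosen once results are known.

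**Working it through.** **Inputs from the documents.** 9 subjects on LTI-03 and 3 on placebo per cohort, so 18 active and 6 pooled placebo (SAP 4.3). Stated chances of seeing an AE among 18 subjects: 60% at a true incidence of 5% and 85% at 10% (SAP 4.3).

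**Inputs assumed.** The documents give no airflow-event rate in IPF subjects and no coding pattern. I take a true incidence p of 10%, 20% or 30%, and cases split equally over k = 1, 2 or 3 PTs, with each affected subject having exactly one PT. A count of at least 2 is used only as a yardstick for visibility; the plan sets no such threshold.

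**Step 1: reproduce the plan's figures.** The chance of at least one event is 1 − (1 − p)^n.
- n = 18: 1 − 0.95^18 = 60.3% and 1 − 0.90^18 = 85.0%. Both agree with the SAP.
- n = 9, one dose: 1 − 0.95^9 = 37.0% and 1 − 0.90^9 = 61.3%.

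**Step 2: one grouped row, p = 20%.**
P(at least 2 of 9) = 1 − 0.8^9 − 9 × 0.2 × 0.8^8 = 1 − 0.1342 − 0.3020 = 56.4%.

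**Step 3: separate PT rows, p = 20%, k = 3.** No row reaches 2 only if every row holds 0 or 1 subject. Summing over j, the number of rows holding one subject, with C(3, j) the number of ways to choose those rows:

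P(no row reaches 2) = Σ C(3, j) × [9!/(9 − j)!] × (0.2/3)^j × 0.8^(9 − j), for j = 0 to 3
= 0.1342 + 0.3020 + 0.2013 + 0.0391 = 0.6767.

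So P(at least one PT row shows 2 or more) = 1 − 0.6767 = 32.3%.

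**Step 4: range.** Chance that a row for one dose shows at least 2 of 9 subjects:

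| True incidence | Grouped row, or all cases under one PT | Any of 2 PT rows | Any of 3 PT rows |
|---|---|---|---|
| 10% | 22.5% | 13.9% | 10.0% |
| 20% | 56.4% | 41.3% | 32.3% |
| 30% | 80.4% | 67.1% | 56.7% |

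**Step 5: a concrete case.** One subject with wheezing and another with chest tightness give two rows of 1/9 (11.1%). A grouped row would show 2/9 = 22.2%, exact 95% interval 2.8% to 60.0%.

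**Step 6: do other planned outputs supply the count?**
- The row for TEAEs leading to discontinuation (SAP 8.1.1) mixes all causes.
- SAP 8.6 gives spirometry means and changes by visit, timepoint and treatment, by-subject graphs showing the 15% FEV1 fall, and a listing. It gives no number of subjects per dose.
- Protocol 9.4.5.1 foresees an incidence of normal-to-abnormal spirometry changes where appropriate. SAP 8.6 does not carry this forward.
- Protocol 8.8 groups similar terms for one monitoring trigger and produces no table.

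**The case against.** The best defence is that the harm remains visible. If investigators record one diagnosis, as Protocol 8.4.1 prefers, a single PT row gives the incidence per dose. An FEV1 fall that meets the criterion in Protocol 6.14.1 stops study drug. A test deterioration that leads to stopping is an AE (SAP 8.1), so such a case enters the discontinuation row by treatment. Spirometry measures the harm directly. With about 24 subjects and every AE listed, nothing is lost from the data. SAP 8.1.1 also follows the SOC and PT summaries specified in Protocol 9.4.4.

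Most of this stands, and it makes splitting a risk, not a certainty. It does not supply the missing count, since none of these outputs gives subjects per dose with an airflow-limitation TEAE.

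A reader might infer three stronger claims that the documents do not support.
- **That Protocol 8.8 would have pooled all such events.** Its wording on similar events covers only unrelated SAEs or Grade 3 or higher AEs in two or more subjects. One related SAE or related Grade 3 event triggers review alone, and non-serious Grade 1 or 2 events are not counted by these triggers. Two of the three Phase 1a cases were moderate.
- **That the harm disappears into an organ class dominated by cough.** Mild dry cough was the most common TEAE in the lower-dose multiple-dose cohorts, but the documents give neither the organ class of the airflow terms nor a cough rate in IPF. PT rows stay visible within any SOC.
- **That a high event rate is expected at these doses.** The dose-limiting events occurred at 40 mg once daily. The protocol describes the lower doses as well tolerated.

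**Conclusion.** The point holds as a gap in presentation: nothing in SAP 8.1.1 to 8.1.3 guarantees a per-dose count of subjects with an airflow-limitation TEAE, although this was the dose-limiting harm in Phase 1a. It would go too far to say that the incidence can appear in no planned row, because consistent coding to one diagnosis would show it.

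At 9 subjects per dose and 20% true incidence, the chance of showing at least 2 subjects falls from 56% in a grouped row to 41% with two PTs and 32% with three. With no splitting the loss is zero. The incidence, the number of PTs and the equal, exclusive split are all assumptions. The equal, exclusive split favours the concern: uneven splitting, or subjects counted under several PTs, would narrow the gap. The figures therefore illustrate the mechanism and do not predict the trial's results. No hypothesis test or error rate is affected. This is a cheap improvement, not a flaw that invalidates the primary analysis.

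**What to change.** Add to SAP 8.1.1 one grouped row, airflow-limitation TEAEs, counting each subject with at least one PT from a pre-specified list. Show n/N, percentage and maximum grade for each dose, active total and pooled placebo, next to the existing SOC and PT tables. Fix the list under blind before unblinding, and preferably before anyone reviews the accumulated AE terms, so that the choice cannot follow the data.

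The cost is a sentence in the SAP, a short term list and one table row. No new data are needed. The downside is some judgement about which terms belong, which is better exercised under blind than afterwards.

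The stopping rules should not change on account of this point. The sponsor should only be asked to reconcile the SAP grouping with the wording on similar events in Protocol 8.8, so that any difference between the two is deliberate and explained.
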